### **7.5 Follow-up Visits**

Subject will undergo a 24-month follow-up period following their final islet transplant. Please refer to the Schedule of Events (Appendices 1, 2, 3, and 4), for the clinical time points of specific follow-up study procedures.

All subjects will follow the Year One Schedule of Events (Appendix 1) in its entirety. Subjects who receive a subsequent islet transplant will continue onto Appendix 2, Continuation of Appendix 1 Schedule of Events (Subjects with Subsequent CIT Transplants) until they reach their one year visit after the final islet transplant. In addition to following Appendix 2, all

subjects who receive a subsequent transplant should complete the assessments listed on the Subsequent Transplant Schedule of Events (Appendix 3), which provides immediate post-transplant and endpoint day assessments. After the one year post-final transplant visit, subjects will move to Appendix 4, Schedule of Events for 1-Year Additional Follow-up.

Subjects are ineligible for subsequent islet transplantation in the CIT04 protocol as of 8 months following their initial transplant (between visits 16 and 17). After visit 21 (365 days following transplant) has been completed, study subjects may obtain a subsequent islet transplant outside of CIT04. Subjects will be followed for adverse events only until until 24 months after their final CIT islet transplant.

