### 4.1.2 Secondary Endpoints

The key secondary endpoint is the proportion of subjects with an HbA1c  $<7.0\%$  AND free of severe hypoglycemic events from Day 28 to Day 365, inclusive, after the first islet transplant.

The other secondary endpoint is the proportion of subjects with an HbA1c  $<7.0\%$  AND free of severe hypoglycemic events from Day 28 to Day 365, inclusive, after the final islet transplant.

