#### 4.1.2.1 SECONDARY EFFICACY ENDPOINTS

At  $75 \pm 5$  days following the first islet transplant and following each subsequent islet transplant:

- The percent reduction in insulin requirements
- HbA1c
- Mean amplitude of glycemic excursions (MAGE)
- Glycemic lability index (LI)
- Ryan hypoglycemia severity (HYPO) score
- Basal (fasting) and 90-min glucose and c-peptide derived from the mixed-meal tolerance test (MMTT)
- $\beta$ -score
- C-peptide: (glucose X creatinine) ratio
- Acute insulin response to glucose (AIRglu), insulin sensitivity, and disposition index (DI) derived from the insulin-modified frequently-sampled IV glucose tolerance (FSIGT) test
- Glucose variability and hypoglycemia duration derived from the continuous glucose monitoring system® (CGMS)
- Quality of life (QOL) measures

If a third transplant occurs less than 75 days after the second transplant, the 75 day endpoint data for the second transplant will not be collected.

At  $365 \pm 14$  days following the first and final islet transplant:

- The percent reduction in insulin requirements
- HbA1c
- MAGE
- LI
- Clarke score
- HYPO score
- Basal (fasting) and 90-min glucose and c-peptide (MMTT)

- $\beta$ -score
- C-peptide: (glucose X creatinine) ratio
- AIRglu insulin sensitivity, and disposition index (DI) derived from the FSIGT test
- Glucose variability and hypoglycemia duration derived from the continuous glucose monitoring system® (CGMS)
- QOL measures
- The proportion of subjects receiving a second islet transplant
- The proportion of subjects receiving a third islet transplant
- Rate of favorable outcome at each center preparing islets (rate of subjects with an HbA1c < 7.0% and free of severe hypoglycemic events)

Secondary efficacy endpoints measured at  $365 \pm 14$  days following the final islet transplant will include the change in the above measures from the results obtained at  $75 \pm 5$  days following the final islet transplant.

At two years (730+14 days) following the final islet transplant:

- The percent change from baseline insulin requirements
- The number of severe hypoglycemic events from 28 days to two years
- HbA1c
- Clarke score
- Basal (fasting) and 90-min glucose and c-peptide (MMTT)
- $\beta$ -score
- C-peptide: (glucose • creatinine) ratio
- CGMS
- QOL

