#### **10.2.2 Secondary Endpoints**

Secondary endpoints are defined in section 4.1.2. There are a very large number of secondary endpoints so there will be no adjustment for multiplicity. We will not impute values for secondary endpoints but will conduct a sensitivity analysis to determine the potential magnitude of the contributions of the missing values. Details of the sensitivity analysis will be included in the SAP.

Analysis of secondary endpoints will use methods similar to those defined for the primary outcome. When the endpoint is a proportion such as patients achieving insulin independence at one year after completing their first islet transplant then the observed rate will be used as the point estimate and an exact 95% binomial confidence interval will be reported. Continuous variables will be treated in a similar fashion. If the necessary normality assumption is valid then the sample mean will be used as the point estimate and the usual 95% normal confidence intervals will be computed. Where the normality assumptions are not valid and an appropriate transform will achieve normality then the inverse of the mean of the transformed data will be used as the point estimate and the inverse of the endpoints for a standard 95% confidence interval for the transformed mean will be reported for the confidence interval. If no valid

transformation can be found then we will use the bootstrap method to construct a point estimate and a 95% confidence interval.

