## 10.4 Sample Size and Power Calculations

The purpose of this pilot study is to estimate the true rate of insulin independence at 75 days. The selected sample size is 10 subjects. The point estimate of the true insulin independence rate will be the proportion of the 10 patients that achieve insulin independence. The precision of the estimate depends on the observed number of subjects achieving insulin independence. The following table displays the confidence intervals that would be computed for each possible outcome. If 5 of the 10 subjects achieve insulin independence then the estimated rate will be 50% and a 95% confidence interval will be 0.1871 to 0.8129. That is, we are 95% confident that the true rate is at least 18.71% and no more than 81.29%. The confidence interval rules out any rate less than 18.71% or greater than 81.29%. If 3 patients (30%) achieve insulin independence, then the confidence interval will rule out any rate less than 6.67% or greater than 65.25%.

*Table 5: Confidence Intervals for each possible outcomes*

Number of Subjects insulin Independent at 75 Days	Estimated Rate	Exact 95% Confidence Interval	
		Lower Bound	Upper Bound
0	0	0	0.3085
1	0.1	0.0025	0.445
2	0.2	0.0252	0.5561
3	0.3	0.0667	0.6525
4	0.4	0.1216	0.7376
5	0.5	0.1871	0.8129
6	0.6	0.2624	0.8784
7	0.7	0.3475	0.9333
8	0.8	0.4439	0.9748
9	0.9	0.555	0.9975
10	1	0.6915	1

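### A transplant outside CIT04 is allowed from Day 365 after the first transplant, but the endpoints anchored on the final transplant have no rule for it

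*Protocol*

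**What the plan says.** All references are to the CIT04 protocol.

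- **Section 7.5, permission.** "After visit 21 (365 days following transplant) has been completed, study subjects may obtain a subsequent islet transplant outside of CIT04". In Appendix 1, visit 21 is Day 365 counted from the first transplant, and Appendix 2 continues from it on the same clock.
- **Section 7.5, follow-up.** The next sentence reads: "Subjects will be followed for adverse events only until until 24 months after their final CIT islet transplant". It does not say which subjects it covers.
- **Section 7.5, cut-off within the trial.** "Subjects are ineligible for subsequent islet transplantation in the CIT04 protocol as of 8 months following their initial transplant". Section 7.6.1 considers subjects with partial graft function for a second transplant from Day 85 up to that limit.
- **Section 4.1.2.** One secondary endpoint is the proportion with HbA1c below 7.0% who are also "free of severe hypoglycemic events from Day 28 to Day 365, inclusive, after the final islet transplant".
- **Section 4.1.2.1.** A set of efficacy measures is due one year after the final transplant and another two years after it. The second set includes "The number of severe hypoglycemic events from 28 days to two years".
- **Section 10.2.2.** "We will not impute values for secondary endpoints"; the same sentence promises a sensitivity analysis for missing values, with details in the SAP. For proportions, "the observed rate will be used as the point estimate and an exact 95% binomial confidence interval will be reported".
- **Section 10.4.** "The selected sample size is 10 subjects".

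**The concern.** The permission to go outside the trial runs on the clock of the first transplant. The endpoints at issue run on the clock of the final transplant. In subjects who had more than one CIT04 infusion the two clocks differ by months, and at two years the permission precedes the assessment in everyone.

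Once a subject has outside islets, two things can happen. The efficacy data may not be collected, in which case the subject drops out of an analysis that does not impute. Or the data are collected, and HbA1c, insulin use or freedom from hypoglycemia partly reflect a graft that is not the one under study. A subject content with the CIT04 graft has little reason to seek another, so both routes would tend to flatter the regimen. With ten subjects, one or two such cases change the reported proportion visibly.

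**Working it through.** **1. The plan's own figures.** Table 5 in Section 10.4 gives exact 95% limits for x successes out of n = 10. The lower limit is the 0.025 quantile of Beta(x, n − x + 1) and the upper is the 0.975 quantile of Beta(x + 1, n − x). For x = 5 this gives 0.1871 to 0.8129, as printed; all 11 rows agree to four decimals. The same method is used in step 4.

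**2. Timeline.** Let t be the day of the final CIT transplant, counted from the first. Eight months is 8 × 365/12 ≈ 243 days. Visit windows are ignored.

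| t | One year after final (365 + t) | Days after visit 21 (t) | Two years after final (730 + t) | Days after visit 21 (365 + t) |
|---|---|---|---|---|
| 0 (one transplant) | 365 | 0 | 730 | 365 |
| 85 | 450 | 85 | 815 | 450 |
| 243 | 608 | 243 | 973 | 608 |

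Put the other way, a subject re-transplanted in that window reaches visit 21 only 365 − 243 = 122 to 365 − 85 = 280 days after the final CIT infusion. A subject re-transplanted before Day 85 because of graft failure has a gap of t, below 85 days. A subject with a single transplant is not exposed at one year but is exposed for the last 365 days before the two-year assessment.

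**3. What is collected after an outside transplant.**

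| Place | What it implies |
|---|---|
| Section 7.5 | Adverse events alone, up to 24 months after the final CIT transplant |
| Sections 8.2.1 and 8.3.1, entry to a non-CIT islet transplant study | AE and SAE collection in CIT stops at that study's intervention |
| Sections 8.2.1 and 8.3.1, standard-of-care transplant at one named site | AEs and SAEs collected until all CIT04 visits are done, which implies that visits continue |
| Appendices 2 to 4 | Full schedules to one and then two years after the final transplant, with no mention of outside grafts |
| Appendix 5 (off study treatment) | HbA1c and MMTT C-peptide at one and two years after the initial transplant; after the last one, only SAEs, hypoglycemic events and QOL |

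These cannot all hold for the same subject. Severe hypoglycemic events are collected with the adverse events (Section 8.2.1), so event-free time under an outside graft can enter the two-year count only where that collection continues.

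Section 10.2.1 shows that the authors saw the issue for the primary endpoint: a late value may replace a missing Day 75 result only if it precedes any further islet transplant, and otherwise failure is imputed. The final-anchored endpoints have no such guard.

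**4. Illustration for the after-final responder proportion.** Assumptions, not in the protocol: 5 true responders of 10, and k non-responders who take an outside graft before the assessment. Counting them as failures gives 5/10 = 50% (18.7% to 81.3%) for every k.

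| k | Dropped: 5/(10 − k) | Credited as successes: (5 + k)/10 |
|---|---|---|
| 1 | 5/9 = 56% (21.2% to 86.3%) | 6/10 = 60% (26.2% to 87.8%) |
| 2 | 5/8 = 63% (24.5% to 91.5%) | 7/10 = 70% (34.8% to 93.3%) |
| 3 | 5/7 = 71% (29.0% to 96.3%) | 8/10 = 80% (44.4% to 97.5%) |
| 4 | 5/6 = 83% (35.9% to 99.6%) | 9/10 = 90% (55.5% to 99.7%) |

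With 3 true responders and k = 3, 30% becomes 3/7 = 43% or 6/10 = 60%.

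Each of the k subjects must have had at least two CIT04 infusions and then an outside one within the gap in step 2. Crediting also requires that HbA1c is still measured and that the subject had no severe hypoglycemic event from Day 28 after the final CIT transplant. Small k is therefore the realistic end of the table.

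**The case against.** Several points on the other side are sound.

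- A reader might infer that the efficacy data are certainly lost. The follow-up sentence names no subgroup. Applied to all subjects it would contradict Appendix 4, and Section 8.2.1 implies that visits go on after a standard-of-care transplant at one site. Loss is one possible outcome, not the stated one for everybody.
- A reader might infer that hypoglycemia-free time on outside islets is always credited to CIT04. Sections 8.2.1 and 8.3.1 stop collection on entry to a non-CIT transplant study, so this holds only on the remaining routes.
- Section 10.1 promises intention-to-treat analysis that accounts for every treated subject, and Section 10.2.2 promises a sensitivity analysis. An observed-only proportion without comment is not clearly what is planned.
- Handling of later events for a lesser secondary endpoint in a ten-subject pilot is commonly left to the SAP. Subjects with an earlier severe hypoglycemic event already count as non-responders, and Section 7.6.1 already classes graft failure after the second transplant as treatment failure.

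These points narrow the concern without removing it. A rule that limits data collection cannot be repaired by a later SAP. The promised sensitivity analysis addresses missing values, not values observed on another graft. The conflict between Section 7.5 and Sections 8.2.1 and 8.3.1 is in the protocol itself.

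**Conclusion.** The concern holds in a limited form. The primary endpoint (Day 75) and the key secondary endpoint (Day 28 to Day 365 after the first transplant) are untouched, so it would be wrong to conclude that the trial's main result is biased. The one-year-after-final measures are exposed only in subjects with more than one CIT04 infusion, by about 85 to 243 days for re-transplants between Day 85 and month 8. The two-year measures are exposed in all subjects, by at least 365 days.

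The direction of bias is upward if those who seek outside grafts are the poor responders. That is an inference. Section 7.6.1 supports it, since a further transplant within the trial is for subjects who have not reached or kept insulin independence. The number who would go outside is not in the protocol, so the illustrated percentages show sensitivity and do not estimate the bias. The point should be corrected, but it does not undermine the design.

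**What to change.** 1. In Section 4.1.2, define the final transplant as the final CIT transplant, so that an outside graft cannot reset the clock.
2. For the after-final responder endpoint, count a non-CIT islet transplant before the assessment as failure and keep the subject in the denominator.
3. End severe-hypoglycemia counts and the matching follow-up time at the date of the outside transplant.
4. Leave continuous values obtained after an outside transplant out of the main summary. Report them, and the last value before it, separately and flagged. The earlier value should not be carried forward: that would be an imputation that Section 10.2.2 rules out, and with a declining graft it could itself flatter the result.
5. Reconcile the visit 21 and follow-up sentences in Section 7.5 with Sections 8.2.1 and 8.3.1 and Appendices 2 to 5, stating which subjects each covers. When an outside transplant is clinically acceptable is not a matter for this review.

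The cost is protocol and SAP wording. The after-final success rate may look slightly less favorable.

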## 7.6 Criteria and Timing for Subsequent Islet Transplants

Subjects who do not meet criteria for a subsequent transplant will enter a reduced follow-up schedule (Appendix 5).

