#### 5.7.1.2 GRAFT FAILURE

Subjects who experience graft failure will be maintained on their current immunosuppressive regimen as long as a subsequent transplant is possible. If/when it is determined that a subject will not receive a subsequent transplant, then immunosuppression will be stopped and the subject will move to the reduced follow-up schedule (see section 5.7.2).

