### 7.6.1 Second Islet Transplant

Islet transplant recipients with partial islet graft function (see Study Definitions) will be considered for a second islet transplant in the interim between 85 days and 8 months post-initial infusion. Islet transplant recipients with **graft failure** will be considered for a second islet transplant before 85 days post-initial infusion. In addition to meeting the criteria outlined below, approval from the Steering Committee must be obtained in advance. Please refer to the MOP for details on this process, which includes review of the potency testing from the first transplant product and post-transplant clinical data.

In order to be eligible for a **second islet transplant**, the following requirements must be met:

1. Subject received  $\geq 5,000$  IE/kg with the first transplant, but failed to achieve or maintain insulin independence.
2. Subject has been compliant with study monitoring and prescribed immunosuppressive therapy.
3. Subject has no unresolved SAEs.
4. No evidence of progressive renal dysfunction, with blood creatinine rising above 2.0 mg/dL (177  $\mu$ mol/L).
5. No evidence of hypersensitization, allergic responses, or other potentially serious drug reactions to medications required by the protocol.
6. PRA  $\leq 50\%$  by flow cytometry (assessment performed locally) and the alloantibody specificity not cross-reactive with antigen(s) present in the subsequent islet preparation in order to avoid unacceptable antigen(s).
7. Absence of any medical condition that, in the opinion of the investigator, will interfere with a safe and successful second islet transplant.

If graft failure occurs after the second islet transplant, these recipients will be considered **treatment failures** with no islet graft function, and immunosuppression will be withdrawn.

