### *Appendix 5: Reduced Follow-up Schedule of Events*

Subjects withdrawn from study therapy should be followed according to the reduced follow-up schedule provided below. All reduced follow-up assessments should be scheduled relative to the day on which the study treatment is discontinued. The last follow-up visit will vary depending on when the subject discontinues study therapy and should be done at 1 year post the subject's **last** transplant.

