#### **REDUCED FOLLOW-UP SCHEDULE**

Complete the following assessments at the intervals (+/- 7 days) indicated below relative to the day the subject discontinued study treatment. Continue conducting these assessments at the defined intervals until the subject reaches two years post **last** transplant.

- Assess SAEs and hypoglycemic events: q1 month. If subject does not come to the study site for the visit, attempt to obtain information via a phone contact.
- Alloantibody (central lab): q 1 month for the first 3 months and q 3 months thereafter.
- Immunogenicity Samples: for subjects who discontinue belatacept, collect samples at 4 weeks and 8 weeks post last dose

Complete the following assessments at 1 and 2 years (+/- 14 days) post **initial** transplant:

- Assess SAEs and hypoglycemic events
- Alloantibody (central lab)
- HbA1c (central lab)
- 90 minute c-peptide post MMTT (central lab)
- Serum creatinine (central lab)
- QOL questionnaire (via mail or in-person)

Complete the following assessments at 1 and 2 years (+/- 7 days) post **last** transplant:

- Assess SAEs and hypoglycemic events
- QOL questionnaire (via mail or in-person)

*Appendix 6: Study Contacts*

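### Section 7.6 moves every subject who cannot be re-transplanted to reduced follow-up, contradicting Sections 5.7 and 7.5 and Appendix 5 and putting most Day 365 secondary measures at risk in functioning grafts

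*Protocol*

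**What the plan says.** The rule in question opens Section 7.6: "Subjects who do not meet criteria for a subsequent transplant will enter a reduced follow-up schedule (Appendix 5". Five other places in the CIT04 protocol bear on it.

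- **Section 7.5** gives the general rule: "All subjects will follow the Year One Schedule of Events (Appendix 1) in its entirety". Subjects then continue on Appendices 2 to 4, with 24 months of follow-up after the final transplant. The same section adds: "Subjects are ineligible for subsequent islet transplantation in the CIT04 protocol as of 8 months following their initial transplant".
- **Section 7.6.1** makes it a condition of a second transplant that the subject received the stated islet dose "but failed to achieve or maintain insulin independence". It considers partial-function recipients from Day 85 to 8 months, and graft-failure recipients before Day 85. Other conditions concern compliance, unresolved SAEs, creatinine, drug reactions and PRA.
- **Section 5.7.1.2** covers graft failure once no further transplant is planned: "then immunosuppression will be stopped and the subject will move to the reduced follow-up schedule".
- **Section 5.7.2** sends subjects who discontinue study treatment early to Appendix 5 and keeps them in the study until its normal end.
- **Appendix 5** defines its own population: "Subjects withdrawn from study therapy should be followed according to the reduced follow-up schedule provided below". It times the recurring assessments from the day treatment stopped. It then gives two end points, both counted from the most recent transplant. One is in the introduction: "The last follow-up visit will vary depending on when the subject discontinues study therapy and should be done at 1 year post the subject's". The other is in the schedule: "Continue conducting these assessments at the defined intervals until the subject reaches two years post".

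**The concern.** Three of these places tie reduced follow-up to graft failure or stopped treatment, and Section 7.5 orders full follow-up for all. Section 7.6 alone uses ineligibility for another transplant as the trigger. That trigger reaches subjects whose graft works and who are still being treated. The natural case is a partial-function subject, considered for a second transplant under 7.6.1 but barred by PRA or an unresolved SAE. Nothing in the protocol stops treatment on that ground alone, and Section 5.1.2.2 continues belatacept to two years after the final transplant. Read literally, the sentence also covers insulin-independent subjects, who cannot meet the first condition of 7.6.1.

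These subjects carry the information on graft function at one year. No text says which section prevails, so the two sites could act differently. Data never collected cannot be restored by any analysis plan. Section 10.2.2 rules out imputation for secondary endpoints, and with 10 subjects each one is 10 percentage points.

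**Working it through.** **1. Who enters, and from what date.** Section 7.6: anyone not meeting re-transplant criteria, with no date given. Section 5.7.1.2: graft failure with no further transplant, immunosuppression stopped. Section 5.7.2: premature discontinuation of study treatment. Appendix 5: withdrawn from study therapy, recurring assessments counted from the stop date. A subject still on belatacept has no stop date, so the monthly and quarterly assessments have no anchor. The visits at one and two years after the initial and last transplants do have one.

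**2. Day 365 efficacy items in Section 4.1.2.1 against the Appendix 5 list.** There are 15 items.

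- Kept after the initial transplant (5): HbA1c, QOL, proportion with a second transplant, proportion with a third, favorable-outcome rate.
- Kept in part (1): MMTT, with 90-minute C-peptide only and no glucose or basal values.
- Not collected (9): insulin reduction, MAGE, LI, Clarke, HYPO, beta-score, C-peptide:(glucose x creatinine) ratio, FSIGT indices, CGMS.

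Check: 5 + 1 + 9 = 15.

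**3. Insulin independence at one year.** The Study Definitions require seven days of glucose and insulin readings, a fasting serum glucose, a 90-minute MMTT glucose, HbA1c and C-peptide. Appendix 5 supplies only HbA1c and the 90-minute C-peptide, so status cannot be determined. Section 2.2 makes reaching and keeping insulin independence the secondary objective, and Section 10.2.2 uses the one-year proportion as its example.

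**4. The two composite secondary endpoints (Section 4.1.2).**

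- *After the first transplant:* Appendix 5 takes central HbA1c at one year after the initial transplant. It assesses hypoglycemic events monthly and again at that visit. Both components remain.
- *After the final transplant, single-transplant subject:* initial and last are the same date, so both components remain.
- *After the final transplant, partial-function subject re-transplanted between Day 85 and 8 months:* 8 x 30.4375 = 243.5 days. One year after that transplant falls between Day 85 + 365 = 450 and about Day 243.5 + 365 = 608.5. Appendix 5 takes HbA1c only at 365 +/- 14 days (Day 351 to 379) and at two years +/- 14 days (Day 716 to 744) after the initial transplant. Neither window reaches the interval, so the HbA1c component is lost.

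**5. Safety.** Section 4.1.2.2 lists GFR reduction, neutropenia, anemia, thrombocytopenia and lipids. Appendix 5 contains no CBC, chemistry panel, measured GFR, lipids, belatacept trough or non-serious AE assessment. It keeps SAEs, alloantibody and, at the visits one and two years after the initial transplant, serum creatinine.

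**6. Effect on precision.** The exact (Clopper-Pearson) limits are: lower = Beta quantile at 0.025 with parameters (x, n - x + 1); upper = Beta quantile at 0.975 with parameters (x + 1, n - x). For x = 5, n = 10 this gives 0.1871 to 0.8129, as Section 10.4 states, and all 11 rows of Table 5 reproduce. Now assume an observed rate of 50% and exclusion of subjects without data:

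| Evaluable | Successes | Exact 95% interval | Width |
|---|---|---|---|
| 10 | 5 | 0.187 to 0.813 | 0.626 |
| 8 | 4 | 0.157 to 0.843 | 0.686 |
| 6 | 3 | 0.118 to 0.882 | 0.764 |
| 4 | 2 | 0.068 to 0.932 | 0.865 |

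The number of subjects affected is not given in the protocol; the rows show a range.

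**The case against.** The best defense is that 7.6 merely points to Appendix 5, whose first sentence restricts it to subjects withdrawn from therapy. Sections 5.7.1.2, 5.7.2 and 7.5 point the same way, so a careful site would probably keep functioning grafts on full follow-up. That stands as far as it goes: the loss is conditional on a site following 7.6. But 7.6 is a mandatory instruction in the section a site consults when re-transplant is refused, and nothing ranks it below the others.

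A reader might infer that all 10 subjects leave full follow-up at month 8, since nobody is eligible after that. The documents do not support this as a working reading. It would empty the later Appendix 1 visits and Appendices 2 and 4, and the paragraph setting the 8-month limit goes on to refer to completing Visit 21 at Day 365. Including insulin-independent subjects is also a literal reading rather than a likely one, because 7.6.1 considers only partial-function and graft-failure recipients. The barred partial-function subject remains on either reading.

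On the end date, the schedule within Appendix 5, Section 5.7.2 and the 24-month follow-up in Section 7.5 outweigh the one-year sentence, so actual loss of second-year data is unlikely. It is still a contradiction.

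**Conclusion.** The contradiction is real and should be corrected. Followed as written, Section 7.6 would cost affected subjects 9 of 15 Day 365 efficacy items and part of a tenth, and the determination of one-year insulin independence. Those re-transplanted from Day 85 on would also lose the HbA1c for the final-transplant composite. Blood counts, chemistry, measured GFR and trough levels would stop while immunosuppression continues.

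It would go too far to say that the Day 365 objectives lose their data. The key secondary endpoint after the first transplant keeps HbA1c and hypoglycemic events under Appendix 5. The Day 75 primary endpoint is largely unaffected: partial-function subjects are considered for a second transplant only from Day 85, and a subject with graft failure already counts as a failure. No sample-size figure changes.

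The conclusion assumes that at least one subject with graft function is refused re-transplant and that the site applies 7.6 rather than 7.5. How many would be affected cannot be derived from the protocol.

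**What to change.** Reconcile Section 7.6 with Sections 5.7.1.2, 5.7.2 and 7.5 and Appendix 5. Limit entry to Appendix 5 to two groups: subjects with graft failure who will not be re-transplanted, and subjects who have discontinued study treatment. State that subjects with full or partial graft function who remain on study treatment continue Appendices 1 to 4, whether or not they qualify for another transplant. This concerns data collection only; it takes no position on who should continue or stop treatment.

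In the introduction to Appendix 5, align the one-year last visit with the two-year follow-up in the schedule below it and in Sections 5.7.2 and 7.5.

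If the sponsor did intend reduced follow-up for some on-treatment subjects, the protocol should name them, give their visits an anchor date and list the endpoints they will not supply.

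The cost is two sentences in an amendment. No visits are added, because Appendices 1 to 4 already schedule them.
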